**For all hypothesis:**

$\mu_1$  is average of measurements with comparator at 2 weeks;

$\mu_2$  is the average of measurements at 2 week follow up (investigational device);

$\mu_3$  is the average of measurements at 8 – 12 week follow up (investigational device);

and  $|M_{NI}|$  is the margin of non – inferiority

**Table 4 Endpoints, test methods and hypotheses**

	Hypothesis	Test Method	Endpoint	Acceptance Criteria
A	Subjects reduced exertion performing 6MWT compared to previous prosthesis (primary outcome)	BORG scale	Mean difference in BORG score pre and post 6MWT compared to comparator	$H_0: \mu_1 \leq \mu_2$ $H_1: \mu_1 > \mu_2$ $p<0.05$
B	Subjects improved performance in 6MWT compared to previous prosthesis.	6MWT (meters)	Average distance walked in 6MWT compared to comparator	$H_0: \mu_1 \geq \mu_2$ $H_1: \mu_1 < \mu_2$ $p<0.05$
C	Subjects report on average no worse support in sit to stand and stand to sit than with previous prosthesis.	Self-report: PMQ (Questions 9 and 10) Likert scale 0-4	Total score of PMQ questions 9 and 10 compared to comparator	$H_0: \mu_1 \geq \mu_2 +  M_{NI} $ $H_1: \mu_1 < \mu_2 +  M_{NI} $ $ M_{NI}  = 1$ $p<0.05$
D	Subjects perceived safety in hill descent is no worse than with previous prosthesis.	Self-report: Modified PEQ 14F (rate your safety when walking down a steep hill using the prosthesis) Likert Scale 1-10	Average score compared to comparator	$H_0: \mu_1 \geq \mu_2 +  M_{NI} $ $H_1: \mu_1 < \mu_2 +  M_{NI} $ $ M_{NI}  = 1$ $p<0.05$
E	Subjects perceived safety in stair descent is no worse than with previous prosthesis.	Self-report: Modified PEQ 13D (rate your safety when walking downstairs using the prosthesis) Likert Scale 1-10	Average score compared to comparator	$H_0: \mu_1 \geq \mu_2 +  M_{NI} $ $H_1: \mu_1 < \mu_2 +  M_{NI} $ $ M_{NI}  = 1$ $p<0.05$
F	Subjects perceive no speed limitation while walking with the investigational device.	Self-report(yes/no): „Are you satisfied with your walking speed using your prosthesis/test prosthesis?”  Support question: “Do you feel that your walking speed is limited by your prosthesis/test prosthesis?”	Proportion of subjects (p) reporting satisfaction with walking speed on investigational device.	$H_0: p < 80\%$ $H_1: p \geq 80\%$ $p<0.05$
G	Subjects reported ability to ambulate over typical environmental obstacles with the investigational device is no worse than with previous prosthesis.	Self-report: PMQ (Question 2-7) Likert scale 0-4 PLUS M	Total score of PMQ questions 2-7 and PLUS M T-score compared to comparator.	For PLUS-M: $H_0: \mu_1 \geq \mu_2 +  M_{NI} $ $H_1: \mu_1 < \mu_2 +  M_{NI} $ $ M_{NI}  = 10T$ For PMQ questions: $H_0: \mu_1 \geq \mu_2 +  M_{NI} $ $H_1: \mu_1 < \mu_2 +  M_{NI} $

				$ M_{NI}  = 3$ $p < 0.05$
H	Subjects safe and stable stance phase perception no worse than previous prosthesis.	Self-report: Modified PEQ 13A (rate your safety (during stance phase) when walking with your prosthesis/test prosthesis) Likert Scale 1-10	Average score compared to comparator	$H_0: \mu_1 \geq \mu_2 +  M_{NI} $ $H_1: \mu_1 < \mu_2 +  M_{NI} $ $ M_{NI}  = 1$ $p < 0.05$
I	Provides comfort in standing no worse than previous prosthesis.	Self-report: PEQ-Question 1D “Rate your comfort while standing when using your prosthesis/test prosthesis” Likert Scale 1-10	Average score compared to comparator	$H_0: \mu_1 \geq \mu_2 +  M_{NI} $ $H_1: \mu_1 < \mu_2 +  M_{NI} $ $ M_{NI}  = 1$ $p < 0.05$
J	The investigational device provides easier setup for CPO compared to previous version of power knee	Self-report: Likert Scale 1-10	Average score compared to previous versions of PK	$H_0: \mu_1 \geq \mu_2$ $H_1: \mu_1 < \mu_2$ $p < 0.05$
K	The investigational device provides no worse ease of setup for CPO compared to SOTA passive MPKs	Self-report: Likert Scale 1-10	Average score compared to SOTA MPKs	$H_0: \mu_1 \geq \mu_2 +  M_{NI} $ $H_1: \mu_1 < \mu_2 +  M_{NI} $ $ M_{NI}  = 1$ $p < 0.05$
M	The investigational device provides acceptable noise level	Self-report: PEQ- Questions 3K, 3L Likert Scale 1-10 Support question (yes/no) “Would the noise from the test device prevent you from preferring it as your usual prosthesis?”	Proportion of participants (p) with average score of PEQ 3K & 3L over 5 with investigational device.	$H_0: p < 80\%$ $H_1: p \geq 80\%$ $p < 0.05$
L	The investigational device provides ease of use of gait functions no worse than previous device	Self-report: PMQ (Questions 1 and 3-6) Likert scale 0-4  Objective measure L-test	Total score of PMQ questions 1, 3-6.  Proportion of subjects (p) successfully completing the L-test using gait functions.	For PMQ score: $H_0: \mu_1 \geq \mu_2 +  M_{NI} $ $H_1: \mu_1 < \mu_2 +  M_{NI} $ $ M_{NI}  = 2,5$ $p < 0.05$  For L-test: $H_0: p < 80\%$ $H_1: p \geq 80\%$ $p < 0.05$
M	Side effects N/A	Side effects	Occurrence of side effects	N/A

N	Mobility using the investigational device is no worse than with the comparator	PMQ total score (0-48)	Average total score of the PMQ	$H_0: \mu_1 \geq \mu_2 +  M_{NI} $ $H_1: \mu_1 < \mu_2 +  M_{NI} $ $ M_{NI}  = 5,5$ $p < 0.05$
O	Activity level increases with longer adaptation period on the investigational device	Activity reports from the knee (daily steps, use time)	Activity level after 8-12w follow up compared to 2w follow up on investigational device	$H_0: \mu_2 \geq \mu_3$ $H_1: \mu_2 < \mu_3$ $p < 0.05$

Informative endpoint: In house usability questionnaire (Perceived weight, size, look, ergonomics, fit w/clothes, battery life, preference, falls questionnaire)

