## 6 Justification for the Design of the Clinical Investigation

The introduction of microprocessor controlled prosthetic knee in 1997 was a major leap in prosthetics in restoring function and increase safety of individuals with a lower limb amputation. Countless studies showed the benefits of such devices, e.g. Hafner et al. and Bellmann et al.. However, such devices are still passive with a major shortcoming, which is that they cannot provide positive power to support the user. In other words, they are unable to generate concentric moments to support the user in situations in which such moments are needed. Standing up and step over step stair climbing are two examples where concentric moments are in principal needed, in order to fulfil these tasks. Although recent passive microprocessor controlled prosthetic knees have been introduced that offer modes which facilitate step over step stair climbing, the power needed still has to be generated by the proximal hip joint of the user. Especially in individuals with a trans-femoral amputation, who may have reduced all over physical capabilities, such modes cannot be used, due to the physical limitations of the user. This fact is for example substantiated by the inclusion criteria in Bellmann et al., who investigated step by step stair climbing in K-Level 3-4 subjects with a passive microprocessor controlled prosthetic knee. Beside in these rather complex movement patterns, knee power is also needed for knee flexion in the swing phase while walking. Although the magnitude of the power needed in this state is rather small, providing power has a pronounced clinical impact, since a reduced clearance in swing is associated with a higher risk of falls.

Several studies have provided evidence for the clinical performance of previous versions of the Power knee (PK), which has the same function and intended use, those are detailed in the Literature review device report [3].

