Results of studies on previous versions of the Power knee indicate that the PK provides support in the sit to stand and stand to sit activity, provides stance phase flexion in level ground walking, support in ascending and descending ramps and stairs and that it does provide active flexion and extension during walking which leads to users being able to walk further and feel less tired. In addition, Pasquina et al. tested the Power Knee as an initial knee prosthesis after combat-related TF amputation or knee disarticulation and found indications that the Power Knee can be helpful as initial prosthesis after TF/KD amputation, participants reached mobility milestones faster than norms identified by expert panel. Shortening the rehabilitation time after amputation has the potential for great savings in healthcare expenditure and large benefits for the patients, e.g. with earlier mobilization and independence. Creylman et al. compared the Power knee and the Rheo knee (passive MPK), their results indicated more symmetric gait with the PK compared to passive MPK.

As the literature shows, a powered prosthetic knee which is able to generate concentric moments is of high interest, to better counterbalance the disability of individuals with a lower limb amputation.

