## 7 Objectives and Hypotheses

The primary objective of this study is to evaluate the efficacy of the investigational device in reducing exertion during walking compared to passive MPKs.

Additionally to evaluate the efficacy of the investigational device in the short and long term compared to passive MPKs and previous versions of the Power Knee, during daily living activities i.e. walking on level ground, in stairs and inclines, rising from and sitting down to a chair as well as performance of gait functions and ease of set up for average to highly active transfemoral/knee disarticulation amputees and CPOs.

No risks or anticipated adverse device effects (ADE) are to be assessed. Any side-effects occurring will be documented.

The hypotheses and endpoints are specified in Table 4.

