## 10 Statistical Considerations

### 10.1 Statistical design and procedures

Outcomes at each timepoint will be visually inspected for normality using histograms and qq-plots. If the data are deemed to be normal the hypotheses will be tested using a two-tailed, paired, student's t-test. Non-normal data will be tested using the Wilcoxon signed-rank test.

Acceptance criteria for the data, as applicable, is defined in Table 4 **Endpoints, test methods and hypotheses**. Subgroup analysis will not be performed as no subgroups are defined.

Repeated measures analysis has the advantage of increased power vis-à-vis group allocations and reduction in error variance associated with individual difference, as each subject acts as its own control. This is important for studying amputees as the group is a small proportion of the total population, and with specific inclusion/exclusion criteria the total eligible population becomes very small, making it difficult to find and recruit subjects to attain an acceptable level of power. This limited population pool often results in slightly heterogeneous sample, as the amputees available are few and far between, in every sense. Furthermore, no single amputation procedure and therefore amputated stump is exactly the same, making the experience of each amputee a bit unique. The within-subject design significantly reduces the individual differences when comparing the two conditions.

The drawback of the design is the potential of "carryover effects", i.e. experience from one condition can affect outcome or performance in the other condition, creating a confounding extraneous variable that varies with the independent variable. Such effects are: practice, positive carryover effect to the latter condition; and fatigue, negative carryover effect to the latter condition.

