## 13 Ethical Considerations

### 13.1 Anticipated clinical benefits

A patient using the investigational device may or may not benefit clinically from using the device as opposed to using another **MPK prosthesis** commercially available. Compared to not using a **MPK prosthesis** the patient will benefit significantly in terms of mobility and ability to live independently. Further on the user will be trained on a new prosthetic component to experience the unprecedented functionality of the new component to mitigate the known deficiencies associated with his amputation. Within the test he/she will be trained on restoring physiological movement pattern closer to those of non-amputees.

Anticipated benefits include, among others: improved step-over-step ramp navigation; reduced effort to sit/stand and reduce likelihood of falls. See chapter 6 for details.

Additionally, the benefit for the user during the testing is that he/she helps in developing a new **MPK prosthesis**.

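### Sit/stand support, a lead reason for the powered knee, is tested only for non-inferiority (Table 4 row C), so no pre-specified benefit conclusion is possible there; a nested superiority step on C, then D, would close the gap

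*Combined protocol and SAP*

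**What the plan says.** Section 6 (Justification for the Design) argues that passive microprocessor knees cannot supply positive power: "Standing up and step over step stair climbing are two examples where concentric moments are in principal needed". It then summarises studies of earlier versions of the device as indicating that "the PK provides support in the sit to stand and stand to sit activity".

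Section 7 adds to the primary objective an evaluation of efficacy in daily activities, including walking "in stairs and inclines, rising from and sitting down to a chair".

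Section 13.1 states: "Anticipated benefits include, among others: improved step-over-step ramp navigation; reduced effort to sit/stand and reduce likelihood of falls".

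Table 4 sets the tests:
- Row C (sit to stand and stand to sit, total of PMQ questions 9 and 10, each scored 0 to 4) begins "Subjects report on average no worse". Its hypotheses are H0: mu1 >= mu2 + |M_NI| against H1: mu1 < mu2 + |M_NI|, with |M_NI| = 1, where mu1 is the comparator mean and mu2 the investigational-device mean.
- Row D (perceived safety in hill descent, scale 1 to 10) "is no worse than with previous prosthesis", in the same form and with the same margin. Row E (stair descent safety) is built the same way.
- Rows A (Borg exertion around the 6MWT, primary) and B ("improved performance in 6MWT compared to previous prosthesis") are superiority tests.

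Section 10.1 sends the reader back to the table for success: "Acceptance criteria for the data, as applicable, is defined in Table 4". Neither section 10 nor Table 4 provides a superiority test after non-inferiority.

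**The concern.** The protocol gives a reason to expect a gain in standing up and sitting down, lists that gain as a benefit and makes it part of an efficacy objective. It then chooses a test that cannot show the gain. Non-inferiority is not a uniform policy of the plan, since walking distance in row B gets a superiority test.

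At stake is the status of a favourable result. If row C comes out strongly positive, the planned reading is still only that the device is no worse, and any statement of benefit would be post hoc. That matters more than usual here because subjects are not blinded (section 9) and the outcome is self-reported, so a reader will give weight to what was fixed in advance.

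**Working it through.** **1. Reproduce the plan's own figure (section 10.2).** Inputs: N = 15 pairs, dz = 0.7084529, one-sided alpha 0.05, Wilcoxon signed-rank test by the A.R.E. method with a normal parent distribution.
- Effective size: N' = 15 × 3/π = 14.324; df = N' − 1 = 13.324.
- Noncentrality: δ = dz × √N' = 0.7084529 × 3.785 = 2.681.
- Critical t (one-sided 0.05) = 1.768.
- Power from the noncentral t = 0.815.

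All of these match section 10.2. The sample size is correct for its own inputs.

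**2. Power of a superiority test on row C or D with the same 15 pairs.** The documents give no SD or effect size for these rows, so dz is an assumption. The critical value is 1.768 one-sided and 2.155 two-sided.

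| Assumed dz | δ = dz × 3.785 | Power, one-sided 0.05 | Power, two-sided 0.05 |
|---|---|---|---|
| 0.5 | 1.89 | 0.56 | 0.42 |
| 0.6 | 2.27 | 0.69 | 0.56 |
| 0.708 | 2.68 | 0.82 | 0.70 |

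Power of 0.80 needs dz of about 0.69 one-sided or 0.80 two-sided.

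On the row C scale (total 0 to 8), one-sided 0.05, by assumed SD of the paired differences:

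| SD | True gain 1 point | True gain 2 points |
|---|---|---|
| 1 | 0.97 | >0.999 |
| 1.5 | 0.77 | 0.999 |
| 2 | 0.56 | 0.97 |
| 2.5 | 0.42 | 0.89 |

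As written, the chance of a pre-specified benefit conclusion on row C is zero by construction.

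**3. What that means for one result.** Suppose a mean gain of 2 points, SD of differences 1.5, N = 15. The standard error is 1.5/√15 = 0.387, and the one-sided 95% lower bound is 2 − 1.761 × 0.387 = +1.32 (p = 0.00007 against zero). Table 4 would still give only the non-inferiority conclusion.

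**4. Type I error within one endpoint.** Non-inferiority is declared when (mean difference + 1)/SE exceeds the critical value, and superiority when (mean difference)/SE exceeds the same value. The second event lies inside the first. A simulation of 400,000 trials of 15 pairs (paired t, one-sided 0.05, SD 1 and 2) gave a false-claim rate of 0.050 at a true difference of −1 and 0.050 to 0.051 at 0. Superiority never occurred without non-inferiority.

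**5. Type I error across endpoints.** The nesting argument does not carry across rows. If six non-inferiority rows (C, D, E, H, I, N) each gained an unadjusted superiority step and all true differences were zero, the chance of at least one false benefit claim would be up to 1 − 0.95^6 = 0.265 for independent endpoints. At correlations of 0.3 to 0.8 it would be about 0.22 to 0.13. Under the plan as written it is none, because no benefit claim is available there.

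With C then D in fixed order, the rate over the two rows stays at the nominal level. If there is no true gain on C, any false superiority claim requires a false rejection on C. If there is a true gain on C, the only possible false claim is on D. Either way the chance is at most alpha.

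**The case against.** Several counter-arguments have force.

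- **The plan does test superiority on a main expected benefit.** Row A is self-rated exertion in walking and row B is walking distance. A reader might infer that no subject-rated activity has a superiority test. That is wrong, because row A has one. The gap concerns sitting and standing and, in part, inclines.
- **The comparator is mixed.** Section 8.2 allows any passive MPK or an earlier Power Knee. Subjects coming from an earlier Power Knee already have powered support, so the section 6 argument predicts little gain for them. Section 13.1 also opens by saying that a patient may or may not benefit relative to another MPK. This makes non-inferiority a defensible first question and may dilute the effect. It does not explain why a gain, if seen, should have no planned test.
- **Most rows do not map to the stated benefits.** A reader might extend the point to every non-inferiority row. Rows D and E rate perceived safety going down a hill or stairs, whereas section 6 speaks of stair climbing and section 13.1 of step-over-step ramp navigation. Rows H and I are not among the benefits listed in section 13.1. Row C maps closely, row D only in part.
- **The data remain usable.** A reader might infer that the trial cannot address benefit in these activities at all. It can: the paired difference and its interval can be reported as exploratory. What is lost is the pre-specified conclusion.
- **The step is not free across rows.** As shown above, adding it unadjusted to six rows would open a risk of false benefit claims that the plan does not now carry. This objection stands and limits the remedy.
- **The power figures are soft.** The dz of 0.708 belongs to the primary endpoint, and a normal-parent formula is only approximate for the sum of two 0 to 4 items.

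**Conclusion.** The point holds for row C and, more weakly, for row D. The protocol presents sit/stand support as a reason for the device, an expected benefit and part of an efficacy objective, but Table 4 permits only a non-inferiority conclusion, whatever the size of the gain. This is a missed pre-specification. It is not a numerical error, and it does not touch the primary analysis or the sample size.

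The opportunity forgone is a test with power of about 0.56 to 0.82 (one-sided 0.05) or 0.42 to 0.70 (two-sided 0.05) at 15 pairs. That rests on assumed dz values of 0.5 to 0.71 and on the normal-parent A.R.E. approximation. The statement that the step costs no alpha is true within an endpoint at a common level, and over C and D only with the fixed order. The documents do not support extending it to E, H, I and N.

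**What to change.** 1. First reconcile section 10.1 (two-tailed test) with section 10.2 (one-tailed calculation), and state the one-sided level at which the directional hypotheses in Table 4 are tested.

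2. Add to Table 4 row C, and to section 10.1: *If non-inferiority is met on row C, superiority (H0: mu1 >= mu2; H1: mu1 < mu2) is tested on the same paired data at the same one-sided level. Superiority on row D is tested only if non-inferiority is met on row D and superiority is met on row C. The paired difference and its confidence interval are reported for both rows.*

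3. Leave rows E, H, I and N as non-inferiority only.

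The cost is a few lines of text, with no extra subjects, visits or measurements, but they must be in place before outcome data are seen. The downside is that superiority claims become possible on secondary, unblinded self-report outcomes with uncertain power. The report should say so, and should describe how many subjects came from an earlier Power Knee.

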### Video

#### Data logging by Össur Logic

See chapter **10.2 Sample size calculation** and **Table 4** for analysis of variables.

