### 10.2 Sample size calculation

Power analysis for the estimated required sample size was conducted using G\*Power. See protocol below:

t tests – Means:	Wilcoxon signed-rank test (matched pairs)
Options:	A.R.E. method
Analysis:	A priori: Compute required sample size
Input:	
Tail(s)	= One
Parent distribution	= Normal
Effect size dz	= 0.7084529
$\alpha$ err prob	= 0.05
Power (1- $\beta$ err prob)	= 0.8
Output:	
Noncentrality parameter $\delta$	= 2.6812808
Critical t	= 1.7676466
Df	= 13.3239449
Total sample size	= 15
Actual power	= 0.8150214

It is therefore expected that **at least 15** subjects are required to complete the protocol with a power of **0.8** and significance at **0.05**. Effect size was estimated for the primary endpoint based on a previous in-house study of the RHEO KNEE, a passive microprocessor controlled prosthetic knee.

Given a drop-out rate of **20%**, up to **18** subjects may be recruited.

For pass/fail criteria, see Table 4 **Endpoints, test methods and hypotheses**.

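### Table 4 tests three single proportions against 80%, but section 10.1 names only paired tests, so the verdict on these rows depends on an unstated choice of test and sidedness

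*Combined protocol and SAP*

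**What the plan says.** Three rows of Table 4 (section 7) concern a proportion measured on the investigational device alone, with no comparator:

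- Row F: "Proportion of subjects (p) reporting satisfaction with walking speed on investigational device".
- Row M (noise; the letter M is used twice in the table): "Proportion of participants (p) with average score of PEQ" items 3K and 3L above 5.
- Row L, second part: "Proportion of subjects (p) successfully completing the L-test using gait functions".

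All three carry the same criterion: the null is a proportion below 80%, the alternative is 80% or more, and p must be below 0.05. The letter p stands for both the proportion and the p-value.

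Section 10.1 says that, for data judged normal, "the hypotheses will be tested using a two-tailed, paired" t-test, and that "Non-normal data will be tested using the Wilcoxon signed-rank test". It names no other test. The end of section 8.1 sends the reader to section 10.2 and Table 4 "for analysis of variables". The Test Method column of Table 4 lists questionnaires and functional tests, not statistical tests. Section 10.2 sizes the primary endpoint only and then closes the loop: "For pass/fail criteria, see Table 4". It plans for at least 15 completers. "Given a drop-out rate of" 20%, it allows up to 18 recruited.

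**The concern.** A paired t-test or signed-rank test compares two measurements on the same subject. For a yes/no outcome on one device set against a fixed 80% there is no pair. Pairing with the previous prosthesis, where that answer exists, would address a different hypothesis. The rule in 10.1 therefore does not fit these rows.

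Several one-sample tests could fill the gap, and at this sample size they disagree on results that could well occur. Section 10.2 gives the rows formal pass/fail status, so a row could be decided by a test picked after the data are known. A lenient choice inflates the chance of passing an inadequate device. A strict choice makes the stated 80% threshold behave like a demand for 100%, which the plan does not tell its readers.

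**Working it through.** **The plan's own figure.** Section 10.2 gives a Wilcoxon matched-pairs calculation: one tail, dz = 0.7084529, alpha 0.05, power 0.8, normal parent. With n' = 15 × 3/π = 14.324, df = n' − 1 = 13.324, noncentrality = 0.7084529 × √14.324 = 2.6813 and critical t = 1.7676, the power is 0.815. This matches the stated N = 15 and 0.8150214. The calculation is for the paired primary endpoint and does not inform the proportion rows.

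**Inputs for the proportion rows.** Null value 0.80 and threshold 0.05 (Table 4); n = 15 completers and at most 18 recruited (10.2). A 20% loss from 18 leaves 18 × 0.8 = 14.4, so n = 14 is also shown, and n = 13 marks the limit.

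**One-sided exact binomial test.** Zero failures: p = 0.8^n. One failure: p = 0.8^n + n × 0.8^(n−1) × 0.2.

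| n | p, zero failures | p, one failure |
|---|---|---|
| 13 | 0.055 | 0.234 |
| 14 | 0.044 | 0.198 |
| 15 | 0.035 | 0.167 |
| 16 | 0.028 | 0.141 |
| 17 | 0.023 | 0.118 |
| 18 | 0.018 | 0.099 |

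From 14 to 18 subjects only a perfect result passes. At 13 not even that does. One failure is first tolerated at n = 22 (p = 0.048), above the recruitment ceiling.

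**Same data, other tests: 14 of 15, observed rate 0.933.**

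- Score: z = (0.933 − 0.8)/√(0.16/15) = 1.29, one-sided p = 0.098. Fails.
- Wald: z = (0.933 − 0.8)/√(0.933 × 0.067/15) = 2.07, one-sided p = 0.019. Passes.
- Exact: p = 0.167. Fails.

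The split holds at both ends of the range. At 13/14 the Wald p is 0.031 and the score p 0.115; at 17/18 they are 0.004 and 0.063.

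**Sidedness: 15 of 15.** One-sided exact: 0.8^15 = 0.0352, which passes. Two-sided exact, adding the lower-tail outcomes no more likely than 15/15 (8 or fewer successes, 0.0181): 0.0352 + 0.0181 = 0.053, which fails. Doubling the one-sided value gives 0.070, which also fails. By the same two-sided method 14/14 gives 0.088 and 16/16 gives 0.055, both failing; 17/17 and 18/18 pass (0.034 each).

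**False passes if one failure is accepted.** At a true rate of exactly 80%, the chance of at most one failure is the right-hand column of the table: 19.8% at n = 14, 16.7% at n = 15, 9.9% at n = 18.

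**Chance of passing under the one-sided exact test.** This is the true rate raised to the power n. The true rates are assumptions; the documents give none.

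| Assumed true rate | n = 14 | n = 15 | n = 18 |
|---|---|---|---|
| 90% | 0.23 | 0.21 | 0.15 |
| 95% | 0.49 | 0.46 | 0.40 |
| 99% | 0.87 | 0.86 | 0.83 |

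**Clopper-Pearson one-sided 95% lower bounds.** 13/13: 79.4%; 14/14: 80.7%; 15/15: 81.9%; 18/18: 84.7%; 14/15: 72.1%; 17/18: 76.2%. They exceed 80% exactly where the one-sided exact test passes.

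**The case against.** The best defence is that any statistician would reach for a one-sample binomial test, that the rows are secondary, and that the exact test errs on the cautious side. The last two points stand and limit the weight of the concern. The first does not settle it, because candidate tests give opposite verdicts at 14/15. Section 10.1's two-tailed convention, if carried over, also reverses the verdict on a perfect 15/15.

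It could also be said that 80% is only an observed threshold, so that 12 of 15 passes. Then the p<0.05 in each row would have no function, unless the shared symbol has caused a slip. The plan needs to separate the two meanings.

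Two stronger readings are tempting and not supported:

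- *The plan imposes a zero-failure rule and cannot succeed at 13 or fewer.* The plan chooses no test. The limit at 13 belongs to the exact test; a one-sided score test passes all-success results from n = 11 (p = 0.049). Nor is 13 a planned number: section 8.3 asks for at least 15 to finish, and reaching 13 from 18 means losing 5, or 28%. Replacement of drop-outs is stated inconsistently (allowed in 8.1, excluded in 8.3). Section 10.3 keeps drop-outs in the analysis for procedures they completed, so a Group 1 subject who leaves after visit 2 can still count in these rows.
- *A failed row shows that the rate is below 80%.* The chances of passing in the working rule this out.

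**Conclusion.** The concern holds: for rows F, L (L-test) and M (noise), the plan assigns tests that cannot address the stated hypotheses, and the available text names no usable one. The consequence is an undetermined pass/fail verdict. One failure in 15 passes or fails according to the test, and no failures in 15 passes or fails according to sidedness. Accepting one failure would raise the false-pass chance at a true 80% rate from at most 5% to between 9.9% and 19.8% over n = 14 to 18.

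The zero-failure requirement is conditional on the one-sided exact test, although a one-sided score test also rejects one failure throughout 14 to 18. The chances of passing rest on assumed true rates. The primary Borg comparison and its sample size are unaffected. This should be corrected, but it does not threaten the trial's main conclusion.

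**What to change.** In section 10.1 and in Table 4 rows F, L (L-test) and M (noise):

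1. Name the one-sided exact binomial test against 80%, alpha 0.05. State that it departs from 10.1's two-tailed rule because the alternative is directional.
2. Use different symbols for the proportion and the p-value.
3. Report each proportion with its Clopper-Pearson one-sided 95% lower bound, so that interval and test agree.
4. State that under this test 14 to 18 evaluable subjects meet the criterion only with no failures, and that 13 or fewer, below the planned 15 completers, cannot meet it.
5. State that a failed row does not show a rate below 80%.

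If the sponsor does not intend a zero-failure rule, the rows can instead be presented as estimates with exact intervals. That is an option, and it would change the acceptance criteria.

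The cost is text only: no added subjects, visits or data. Because the change concerns endpoints, the simple-notification route in section 11.1 does not appear to fit. An amendment with sponsor approval and IRB review should be expected, made before the data are seen. The downside is a weaker formal claim on these secondary rows.
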